15.8 Run-in period (day -28 or -14, to -1)

Eligible subjects after screening, will be asked to refrain from taking any medication or supplement to relieve their constipation. Subjects will complete the eDiary every day before bedtime. Subject's eligibility according to inclusion #3 will be determined based on 14 consecutive days.

In the eDiary the subjects will be asked to report on their:

- · Daily BM,
- Change of diet, if applicable (NOTE: the protocol will not ask the patient to change anything in his/her diet. any change of diet will be recorded in the eDiary)
- Change in symptoms as: Bristol stool consistency, straining, bloating, and the other questions in the eDiary
- Medication
- change in general health condition

The run-in period may be extended by a few days in case of technical issue (difficulty to access eDiary or in case a clear decision cannot be made), to allow for a wash-out period, or other. The run-in period may be extended by up to 14 days.

In case of extension, the last 14 consecutive days of the eDiary will be monitored to determine eligibility of the subjects (based on inclusion #3). Subjects need to have an average of \geq 1 SBM and \leq 2.5 SBM per week during the two weeks of run-in for eligibility. In any case, subjects should have at least 1 SBM and not more than 3 SBMs during each of the run-in weeks.

Doc No: 280CLD

Rev: 01 Date: 24 May 2021

Page 51 of 103

The study coordinator will monitor the e-diary of each patient to confirm patient's compliance and that data entered is clear. The subjects will receive a short phone call as needed from the study coordinator.

The phone calls may include clarification re eDiary entries, resolving issues of subject compliance with the eDiary, occurrence of adverse events, use of rescue medication, subject understanding of what he/she needs to do in the context of the study and discussion of any issue or difficulty that the subject might have. Documentation of the date and time of the phone call will be reported on the eCRF.

Subjects that miss to complete 3 days (or more) of the e-diary (not due to technical issues) during the run-in period, may be considered as screening failures due to lack of compliance.

During the run in (as well as throughout the whole study period) subjects will need to adhere to rescue medication rules (see section 15.12). Subject that used 3 rescue meds (or more) during the run in period will be considered a screening failure.

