17.2 Study Endpoints

17.2.1 Primary Efficacy Endpoint

There are two primary efficacy endpoints for this study.

The two primary efficacy endpoints are the CSBM1 success rate, defined as an increase from the run-in period of at least one weekly Complete Spontaneous Bowel Movement (CSBM) during at least 6 of the 8 weeks of treatment, and CSBM2 success rate, defined as an increase from the run-in period of at least two weekly Complete Spontaneous Bowel Movement (CSBM) during at least 6 of the 8 weeks of treatment.

The study will be deemed successful if either the CSBM1 or the CSBM2 success rate is statistically significantly higher in the active arm, than in the placebo arm.

Doc No: 280CLD Rev: 01 Date: 24 May 2021

Page 66 of 103

17.2.2 **Secondary Efficacy Endpoints**

Secondary efficacy endpoints include:

- Change from baseline in average straining. 1.
- 2. CSBM1 expanded success rate, defined as an increase from the run-in period of at least one weekly Complete Spontaneous Bowel Movement (CSBM) during at least 5 of the 8 weeks of treatment.
- Change from baseline in average stool consistency, using the Bristol Stool Scale 3.
- 4. CSBM2 expanded success rate, defined as an increase from the run-in period of at least two weekly Complete Spontaneous Bowel Movement (CSBM) during at least 5 of the 8 weeks of treatment
- 5. Change from baseline in average bloating.

17.2.3 **Additional Efficacy Endpoints**

Additional efficacy endpoints include:

- SBM success rate, defined as an increase from baseline at least one weekly spontanuous Bowel Movement (SBM) during at lease 6 out of 8 weeks of treatment.
- Incidence of Rescue Medication use during the treatment period.
- Change from baseline in weekly number of Spontaneous Bowel Movement (SBM).
- Change from baseline in weekly number of Complete Spontaneous Bowel Movement (CSBM).
- Rate of SBM < 24 hours after first dose
- Change from baseline in average abdominal gas.
- Change from baseline in average abdominal pain.
- Change from baseline in abdominal discomfort.
- Time to occurrence of spontaneous bowel movement after first capsule activation.
- Change from baseline in quality of life using the PAC-QOL (Patient Assessment of Constipation Quality of Life) questionnaire.

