17.9 Statistical Analysis

17.9.1 General Considerations

Statistical analyses will be performed using SAS® v9.4 or higher (SAS Institute, Cary NC, USA).

Baseline demographic and other baseline characteristics, together with safety analyses will be performed on all enrolled subjects.

Baseline values are defined as the last valid value prior to treatment.

All statistical tests will be two-sided. If statistical tests are performed nominal p-values will be presented. Where confidence limits are appropriate, non-adjusted two-sided 95% confidence interval will be constructed.

For comparison of means (continuous variables), the two-sample t-test or the Wilcoxon rank sum test will be used as appropriate. For comparison of proportions (categorical variables), the Chi-squared test or Fisher's exact test will be used as appropriate.

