17.9.5 Efficacy Analysis

Doc No: 280CLD Rev: 01 Date: 24 May 2021

Page 73 of 103

The subject's CSBM1 success status (i.e. if the subjects achieve an increase from baseline of at least 1 weekly CSBM during at least 6 out of the 8 treatment weeks) will be presented in tabular form by study arm, along with 95% Wilson score Confidence Intervals (CI) and will be compared between the study arms with a Cochran-Mantel-Haenszel test controlling for center.

The CSBM2, the expanded CSBMs and the SBM success rates will be analyzed in a similar manner.

The incidence of rescue medication and the rate of SBM within 24 hours from the first study dose use will be analyzed in a similar manner.

The change from baseline in average straining will be modeled with an Analysis of Covariance (ANCOVA) model, with baseline average straining and site entered as covariates. The adjusted means of the change from baseline per study arm, and the difference between the groups will be presented along with respective 95% CI. The change from baseline in average stool consistency, in average bloating, in weekly number of SBM and CSBM, and in symptoms will be analyzed with similar ANCOVA models.

Time to occurrence of SBM after intake of the first Vibrant capsule (either active or placebo) will be assessed and presented by Kaplan-Meier curves and will be compared between the study arms using the Log-Rank test if relevant.

Treatment satisfaction, and incidence of use of rescue medication will be presented in tabular form.

The PAC-QoL, the rescue medication use, and the rate of SBM during the first 24 hours after the first dose will be presented in tabular form.

17.9.6 **Treatment by Center Interaction**

Poolability will be tested in the primary analysis at a significance level of 10%.

Poolability across centers, for the primary endpoints, will be assessed using a logistic regression model.

Centers will be grouped together by geographical area, a table of the sites and their geographical area within and without the USA will be presented. If found significant, the reason for the significance would be further explored and rationalized. This evaluation may include demographic features, symptoms at presentation, clinical and treatment history, and site comparability in the features found to be associated with the primary performance variable.

Doc No: 280CLD	
Rev: 01	Date: 24 May 2021
Page 74 of 103	

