17.9.8 Handling of Missing Data

Subjects with less than 6 weeks of diary data will be considered as failures for the CSBM and SBM success rates, as the primary imputation method for missing data.

Additional sensitivity analysis of the primary end-point will be performed to assess the impact of missing data on the study outcome using possible imputation methods for binary data:

- Multiple imputation for binary data.
- Observed Data: Use only subjects with 8 weeks of non-missing diary data and who did not withdraw early from study.
- Best Case Scenario: Assume all subjects with missing data in study group are successes; Assume all subjects in the placebo group with missing data are failures.
- Worst Case Scenario: Assume all subjects with missing data in study group are failures; Assume all subjects in the placebo group with missing data are successes.

In addition, for missing diary day, the number of bowel movement will be imputed to "0", and the intake of rescue medicine to "No". For the time to first SBM analysis, subjects with no known SBM will be considered left censored.

For the analyses of the other endpoints, no imputations for missing values will be performed.

Doc No: 280CLD

Rev: 01 Date: 24 May 2021

Page 75 of 103

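### The plan does not say how blank diary days enter the weekly SBM and CSBM counts; if they count as zero, the two change-from-baseline frequency endpoints are biased, in a direction that depends on where the gaps fall

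*Combined protocol and SAP*

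**What the plan says.** Bowel movements are known only from the daily eDiary (sections 15.1 and 15.9). Section 17.2.3 lists the changes from baseline in weekly number of SBM and of CSBM as additional efficacy endpoints. Under section 17.9.5 the changes "in weekly number of SBM and CSBM, and in symptoms will be analyzed with similar ANCOVA models", that is, adjusted for the baseline value and site.

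Section 17.9.8 contains two sentences that could govern these endpoints:

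- At day level, "for missing diary day, the number of bowel movement will be imputed to" zero "and the intake of rescue medicine to" No. No endpoint or study period is named.
- In closing, "For the analyses of the other endpoints, no imputations for missing values will be performed". The section has by then named the CSBM and SBM success rates and the time to first SBM, but not the changes in weekly number.

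Three other passages bear on completeness:

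- Section 17.9.1: "Baseline values are defined as the last valid value prior to treatment". This does not say how a weekly rate is formed from a 14-day run-in.
- Section 17.8.3 requires at least two treatment weeks with five or more diary days, but only for evaluability in the mITT set.
- Section 15.8: subjects who miss three or more run-in diary days, other than for technical reasons, "may be considered as screening failures due to lack of compliance".

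The sensitivity analyses for missing data in section 17.9.8 concern the primary endpoint only.

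**The concern.** A blank diary day is a day without observation, not a day without a bowel movement. For a mean-rate endpoint the two differ: a subject with 4 SBM per week and one blank day each week scores 4 x 6/7 = 3.43 if the blank day counts as zero. The ANCOVA would then estimate a mixture of bowel frequency and diary completion.

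The closing no-imputation sentence does not settle this. The plan gives no formula, denominator or minimum of recorded days for a weekly number. If a five- or six-day week is simply added up, its blank days count as zero even though nothing has formally been imputed.

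At stake are the two endpoints that express benefit in movements per week. They do not decide whether the study succeeds, but they are likely to be read as the size of the effect, and no planned analysis would show how far diary gaps had moved them.

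**Working it through.** **Stated figures.** The plan gives none for these endpoints. Its sample size for the success rates (12% versus 40%, two-sided 2.5%) does reproduce: 46 per arm, power 80.7%. The point does not depend on it.

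**Inputs from the plan.** Run-in SBM between 1 and 3 in each week, averaging 1 to 2.5; 14 run-in days assessed; up to 2 missed run-in days fall below the screening-failure threshold; 8 treatment weeks.

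**Assumed inputs.** True treatment-period rates and all missing fractions. The plan gives no expected diary completion.

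**Bias in the within-arm change.** If missing days are unrelated to bowel movements and are scored 0, the expected change is T(1 - f_t) - B(1 - f_b). Subtracting the true change T - B leaves

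bias = -T x f_t + B x f_b.

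With B = 2 and T = 3 (true change +1.00):

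| Run-in days missing (of 14) | Days missing per treatment week | Bias |
|---|---|---|
| 0 | 1 | -3/7 = -0.43 |
| 2 | 1 | -3/7 + 2 x 2/14 = -0.14 |
| 2 | 0 | +2 x 2/14 = +0.29 |

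With 2 run-in days missing, the sign changes at f_t = B x f_b / T = 2 x (2/14) / 3 = 0.095, or 0.67 days per treatment week. Over B from 1 to 2.5, T from B to B + 2, and 0 to 2 days missing in the run-in and in each treatment week, the bias runs from -4.5 x 2/7 = -1.29 to +2.5 x 2/14 = +0.36.

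A second set, with B = 1.8 and T = 3.8 active (true change +2.0):

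- Run-in completion 95%, treatment completion 95% / 90% / 86%: 3.61 - 1.71 = 1.90; 3.42 - 1.71 = 1.71; 3.27 - 1.71 = 1.56.
- Run-in 12 of 14 days, treatment 95%: 3.61 - 1.54 = +2.07, above the true value.

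**Bias in the arm difference.** The run-in precedes randomization, so B x f_b is expected to be equal in the arms and cancels, leaving -T_a x f_a + T_p x f_p.

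- Equal completion c: the difference is c(T_a - T_p). With 3.8 versus 2.8 (true 1.0) it is 0.95, 0.90 or 0.86 at completion 95%, 90% or 86%.
- Unequal completion, with 3.5 versus 3.0 (true 0.50):

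| Missing, active / placebo | Expected difference |
|---|---|
| 5% / 5% | 3.325 - 2.850 = 0.475 |
| 10% / 10% | 3.150 - 2.700 = 0.45 |
| 5% / 10% | 3.325 - 2.700 = 0.625 |
| 10% / 5% | 3.150 - 2.850 = 0.30 |
| 15% / 5% | 2.975 - 2.850 = 0.125 |

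**Withdrawal, only if later days are also scored 0.** With the same rates, withdrawal half-way, and 15% active versus 5% placebo, the shift is -3.5 x 0.15 x 0.5 + 3.0 x 0.05 x 0.5 = -0.19. With the withdrawal rates reversed it is -3.5 x 0.05 x 0.5 + 3.0 x 0.15 x 0.5 = +0.14.

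**Rate per recorded day.** In a Poisson simulation with B = 2 and T = 3, the three patterns in the first table gave zero-rule changes of 0.57, 0.86 and 1.28. Scaling by recorded days gave 0.99 to 1.01. That recovery is built in, because the simulated gaps were independent of bowel movements. It confirms the algebra and says nothing about how real gaps arise.

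**The case against.** The strongest reply is that the plan never applies the zero rule to these endpoints. They are not named in section 17.9.8, so they can be read as other endpoints with no imputation. That makes the scope of the rule unclear but does not remove the problem. On its natural day-level reading the zero rule feeds every weekly count, and without a stated derivation an unscaled partial week gives the same number.

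Three stronger inferences are tempting, and the documents do not support them.

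- **That the change is always biased downward.** The zero rule is not confined to treatment, so zero-filled run-in days lower the baseline and raise the change. Setting unrecorded rescue use to No can also let a movement after rescue count as spontaneous. Nor do the documents show that gaps fall mainly in the treatment period: a daily alert is set (section 15.7), diary completion is reviewed at weeks 4 and 8 (sections 15.10 and 15.11), and non-compliance can end participation (section 28).
- **That weekly numbers are totals over seven calendar days.** No section gives this or any other formula.
- **That days after withdrawal become zeros.** Section 17.9.8 speaks of a missing diary day and does not extend this past withdrawal. Without that step, and with equal completion, the difference is c times its true value essentially whatever the withdrawal rates, apart from partial weeks.

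It is also fair to object that scaling by recorded days is itself a modelling choice. If subjects skip entries on days without a movement, or if non-responders leave, it overstates the rate. This stands as a real limitation of the remedy.

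**Conclusion.** The concern holds as a gap in the plan with a conditional bias. Section 17.9.8 contains two sentences that conflict for these endpoints, and the weekly number is undefined. If blank days count as zero by rule or by unscaled summing, the within-arm change is off by -T x f_t + B x f_b, from -1.29 to +0.36 movements per week over the ranges examined. The arm difference shrinks in proportion to completion when the arms are equal and moves either way when they are not. All of these sizes rest on assumed rates and missingness, with gaps unrelated to bowel movements.

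A reader might infer a demonstrated downward bias, or a large distortion from unequal withdrawal. The text supports neither: the first depends on where the gaps fall, and the second requires scoring days after withdrawal as zero, which the plan does not state. The two endpoints lie outside the hierarchy of section 17.9.2.3, so this point does not touch the criterion for study success. It should be corrected because the correction is cheap and these are the endpoints that describe effect size in natural units.

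**What to change.** In section 17.9.8, state that the zero rule does not apply to the changes in weekly number of SBM and CSBM, and define the derivation:

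- Weekly rate = 7 x (SBM or CSBM on completed diary days) / (completed diary days), in the run-in and in each treatment week with at least five completed days, borrowing the threshold of section 17.8.3.
- Treat all other treatment weeks, including those after withdrawal, as missing, and average the valid weeks.
- Keep the zero rule for these endpoints as a sensitivity analysis.

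The cost is a few lines of SAP text and simple reprogramming, with no new data. The downside is the assumption that unrecorded days and weeks resemble recorded ones in the same subject. Rates may be overstated if entries are skipped on days without a movement or if non-responders withdraw. The retained zero-rule analysis shows how much this matters.

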17.4 Sample size

A sample size is calculated to test the null hypotheses. Calculations (using SAS® proc power) show that a sample size of 92 subjects (46 in each study arm), would provide 80% power at a study wise 5% level of significance (two-sided), i.e., 2.5% for each one of the primary endpoints to detect a difference of 28% in the success rate, assuming a success rate of 12% in the placebo arm.

The sample size will be increased to at least 102 subjects (51 in each study arm) to account for a potential 10% of drop-out rate.

Doc No: 280CLD

Rev: 01 Date: 24 May 2021

Page 68 of 103

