17.9.2.3 Hierarchy Approach for Secondary Endpoints Analysis

The hierarchy approach will be adopted for the primary and secondary endpoints to control type I error due to multiple endpoints testing. Thus, the primary endpoint will first be analyzed and only if at least one of them is found statistically significant, will the secondary endpoints be analyzed.

The first secondary endpoint will be tested, first, for statistical significance and only if found significant (versus an alpha level of 5% if both primary endpoints are found statistically significant, or 2.5% if only one of the two primary endpoints is found statistically significant), the next in line will be tested. Only if the first and second secondary endpoints are found statistically significant, then the third one will be tested, and so on.

The order of the secondary endpoints is as listed in paragraph 17.2.2.

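### Minor: the time-to-first-SBM analysis labels subjects with no recorded SBM as left censored, but the planned Kaplan-Meier and log-rank methods need right censoring at a named time

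*Combined protocol and SAP*

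**What the plan says.** Section 17.2.3 lists among the additional efficacy endpoints: "Time to occurrence of spontaneous bowel movement after first capsule activation". Section 17.9.5 gives the method: "Time to occurrence of SBM after intake of the first Vibrant capsule (either active or placebo) will be assessed and presented by Kaplan-Meier curves", and the curves "will be compared between the study arms using the Log-Rank test if relevant".

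Section 17.9.8 gives the rule for subjects without an event: "subjects with no known SBM will be considered left censored". It states no censoring time. The sentence before it says that "for missing diary day, the number of bowel movement will be imputed to" zero, and that rescue intake on such a day is set to no. No other section corrects the word left or says when event-free follow-up ends.

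On the standing of the endpoint, section 17.9.2.3 limits the hierarchy to the primary and secondary endpoints ("The order of the secondary endpoints is as listed in paragraph 17.2.2"), and section 17.9.1 says: "If statistical tests are performed nominal p-values will be presented".

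**The concern.** Time runs forward from the first capsule. If the diary of a subject shows no SBM, the first SBM, if there is one, lies after the last observation. That is the definition of right censoring, and it is what the standard Kaplan-Meier and log-rank methods take as input. Left censoring means that the event took place at some unknown moment before the recorded time.

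A programmer therefore has two options. One is to follow the text, which turns subjects with no observed response into responders. The other is to set an ordinary right-censoring flag, which gives the intended analysis but departs from the written plan. Because no censoring time is named, even the second option leaves a choice open. A subject who stops the diary early could be censored at the last entry. Alternatively, through the zero rule for missing days, the subject could be carried as event-free to the end of treatment.

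**Working it through.** The plan gives no figure for this endpoint, so there is nothing to reproduce. The check has two parts.

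**1. What the literal rule does to the curve**

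Take an arm of n subjects. Suppose k of them are followed to day 56 with no SBM, and all the others have one.

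- Right censored at day 56: SBM-free proportion at day 56 = k/n.
- Left censored at day 56: every subject is taken to have had the event by day 56, so the SBM-free proportion is 0 whatever k is.

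With n = 51 (section 17.4) and k = 1, right censoring gives 1/51 = 2.0% and left censoring gives 0%. With k = 3 the figures are 3/51 = 5.9% and 0%. A left-censored (Turnbull-type) estimate confirms the zero in each case. The values of k are illustrative.

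For a subject who leaves early the end of the curve may not differ. If another subject's first SBM comes after that subject's last observation, the right-censored curve can also fall to zero. The difference then lies in the earlier part of the curve.

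**2. How many subjects this could concern**

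Inputs from the documents:

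- Run-in average of 1 to 2.5 SBMs per week (section 14.1, inclusion criterion 4).
- Planned size: "at least 102 subjects (51 in each study arm) to account for a potential 10% of drop-out rate" (section 17.4). Ten per cent of 51 is about 5 drop-outs per arm.
- Subjects with less than 2 weeks of valid diary are non-evaluable in the modified intent-to-treat (mITT) set (section 17.8.3), which is the main efficacy set (section 17.8.5).

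Assumptions not in the documents: SBMs follow a Poisson process at the run-in rate, and all 5 drop-outs leave at week 2, the earliest point compatible with the mITT rule.

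P(no SBM by week t) = exp(-rate × t)

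| Rate per week | P(no SBM by week 2) | Expected number among 5 drop-outs | Divided by 51 |
|---|---|---|---|
| 1 | exp(-2) = 0.135 | 0.68 | 1.3 points |
| 2.5 | exp(-5) = 0.0067 | 0.03 | 0.07 points |

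The last column is an upper bound. Recoding one right-censored subject as an event raises the estimated event proportion by at most 1/n = 1/51 = 2.0 points, and reaches that only if the event is placed early.

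Subjects who complete 8 weeks contribute almost nothing. At 1 SBM per week, exp(-8) = 0.0003, so among 46 completers the expected number with no SBM is 46 × 0.000335 = 0.015. At higher rates it is smaller still. The day-56 illustration in part 1 therefore shows the direction of the error and is not a likely result. Clustered bowel movements, or the rule in section 13.1 that an SBM must come at least 48 hours after rescue, could raise these counts. The documents give no figure from which to say by how much.

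**The case against.** The strongest reply is that this is a slip of one word. Kaplan-Meier and log-rank routines take right-censored data, so the literal text cannot be run with the planned methods, and a silent wrong analysis is unlikely. That stands, and it is the reason for grading the point as minor. It does not remove the point: the sentence is a stated analysis rule, it is wrong as it reads, nothing else in the document corrects it, and it names no censoring time.

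A reader might infer that the rule could decide whether the log-rank test is significant. The documents do not support that. They give no time-to-first-SBM data, and the result depends on where in the left-censored interval the event is placed. In a constructed example with 46 per arm, assumed rates of 2.5 (active) and 1.75 (placebo) per week, first-SBM times at exponential quantiles and one placebo subject with no SBM to day 56, right censoring gives p = 0.049. Placing the event near time 0 gives 0.114. Placing it at day 56 gives 0.049 again, and placing it at each of the placebo arm's own event times gives 0.049 to 0.113. The contrast with time 0 is the extreme case only, and a completer with no SBM is very unlikely under the same model.

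A reader might also take drop-out at week 1 as the relevant case. Then 5 × exp(-1) = 1.84 or 5 × exp(-2.5) = 0.41 subjects per arm would have no SBM, a bound of 3.6 or 0.8 points. Those subjects have less than 2 weeks of diary and are non-evaluable in the mITT set, so these figures bear only on the supporting ITT presentation.

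Finally, it might be argued that zero imputation of missing diary days must not extend event-free follow-up. That is partly a preference. The zero rule could equally be read as supporting censoring at the end of treatment. What the plan lacks is a statement of which is meant.

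**Conclusion.** The point holds as a minor error in wording with a gap beside it. Section 17.9.8 assigns the wrong kind of censoring for the methods in section 17.9.5 and names no censoring time. If followed to the letter, it would count subjects with no recorded SBM as having had one.

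The reach is narrow. The binary endpoint of an SBM within 24 hours does not use the rule. The primary endpoints, the secondary hierarchy, the sample size and the interim rule do not depend on it. In the main efficacy set the expected shift in a curve is at most about 0.07 to 1.3 percentage points. That size rests on the Poisson assumption at 1 to 2.5 SBMs per week and on 5 drop-outs per arm, all at week 2. The conclusion that the word is wrong follows from the definition of censoring and needs none of these assumptions.

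**What to change.** In section 17.9.8, replace left censored with right censored and name the censoring time. The last completed eDiary entry and the end of treatment are both workable, and the choice is the sponsor's. Add one sentence saying how that time fits with the rule that sets missing diary days to zero bowel movements, so that a subject who stops the diary early is handled in one prespecified way. If the last entry is chosen, an SBM on an earlier missing day would still go unseen, which is a small limitation worth stating.

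The cost is one replaced sentence and one added sentence, best made before unblinding. Data collection, sample size, and the primary and secondary analyses do not change.
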